6. STATISTICAL METHODS

The primary objective of the study is to determine whether 6 months of neoadjuvant apalutamide prior to prostatectomy for intermediate risk prostate cancer can result in a reduction of "aggregate pathologic risk features" (APRF) that drive post-operative radiotherapy recommendations. We hypothesize a reduction of 20% (i.e., from 35% to 15%) in terms of the rate of APRF among intermediate risk patients. Using a one-sample exact binomial test and with a two-sided type I error of 0.05, a sample size of 41 patients would provide 84% power to detect this change. We would factor up to

10% additional enrollment for compliance issues, thus the total enrollment from MDACC will be up to 45 patients.

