6.3 Interim Analysis

The standard therapy for intermediate risk prostate cancer patients is radical prostatectomy. In the current trial, we are treating patients with apalutamide for 6 months in the neoadjuvant setting followed by the standard radical prostatectomy, thus we do not anticipate the rate of APRF(aggregate pathologic risk features) to be higher than the 35% rate with radical prostatectomy alone. Therefore, no interim analysis for futility is planned.

Monitoring for safety will be implemented in this single arm trial with the benchmark of avoiding extreme toxicities (TOX), defined as any adverse event preventing surgery or treatment-related death before surgery. Patients who voluntarily leave the trial for any reasons, or are successfully treated with dose reductions and proceed with surgery will not be counted as having a TOX. Denote the probability of TOX by θ_T and a beta(0.6, 1.4) distribution was assumed for the prior. Our stopping rule is given by the following probability statement: Pr ($\theta_T > 0.30$ | data) >0.90. That is, we will stop the trial if, at any time during the study, we determine that there is more than a 90% chance that the TOX rate is more than 30%. The corresponding stopping boundaries are shown in Table 1 below and the operating characteristics of the toxicity monitoring are illustrated in Table 2. Multc Lean Desktop (v2.1.0) was used for generating the stopping boundaries and the OC table.

Table 1. Interim toxicity stopping boundaries in cohort size of 5.

Among These Number of	Stop the trial if these many
Patients	patients with toxicities
5	4-5
10	6-10
15	8-15
20	9-20
25	11-25
30	13-30
35	15-35
40	16-40
45	18-45

Table 2. The operating characteristics of toxicity monitoring.

True Toxicity Rate	Prob (stop early)	Average number of patients
0.1	0.0006	44.98
0.2	0.02	44.32
0.3	0.21	39.70
0.4	0.66	28.55
0.5	0.95	17.57

An Efficacy/Toxicity Summary will be submitted after the first five evaluable patients complete 24 weeks of study treatment, and every five patients thereafter. The Investigator is responsible for completing the summary report and submitting it to the IND Office Medical Monitor for review.

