- Subjects experiencing toxicity considered to be related to the use of for which more than two dose reductions areneeded will require discontinuation of study drugs.

Withdrawal from Study

An investigator may withdraw a patient from the study at any time based on clinical judgment or if a patient withdraws consent. In this event, the reason(s) for withdrawal must be documented and clarification if withdrawal of consent includes Post-Radical Prostatectomy Evaluation data collection. A patient's decision to take part in the study is voluntary and he may choose not to take part in the study or to stop taking part at any time. If he chooses not to take part or to stop at any time, it will not affect his future medical care or medical benefits. A patient may withdraw from study treatment phase for any reason. In general, subjects who withdraw will not be replaced unless the number of completed subjects falls below the estimated sample size required to provide the desired precision.

Radical Prostatectomy

Within 2 weeks of stopping apalutamide, patients will undergo planned radical prostatectomy. The surgical access is per the attending surgeon discretion such as open or robot-assisted. The extent of primary surgery such as inclusion/exclusion of the neurovascular bundles and bladder neck is per attending surgeon discretion. The seminal vesicles should be completely removed if possible. The lymph node dissection should attempt to consist of an extended template, specifically: a) obturator fossa, b) external iliac from the medial aspect of the external iliac artery and clearing the triangular space at the junction of the external and internal arteries, c) hypogastric artery to include a continuation of the obturator fossa beneath the obturator nerve. The protocol does not require the surgeon to deviate from his/her common practice and judgment in the event unexpected grossly enlarged lymph nodes are encountered.

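### The toxicity count in section 6.3 excludes every voluntary leaver whatever the reason, so the only numerical stopping rule can miss an adverse event that prevented surgery

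*Combined protocol and SAP*

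**What the plan says.** Section 6.3 (Interim Analysis) sets up Bayesian monitoring of one event, TOX, "defined as any adverse event preventing surgery or treatment-related death before surgery". The sentence that follows takes two groups out of the count. The first is "Patients who voluntarily leave the trial for any reasons". The second is men who "are successfully treated with dose reductions and proceed with surgery will not be counted as having a TOX".

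Nothing in the section says what happens when a man satisfies both the definition and the first exclusion. Nor does it say whether a voluntary leaver stays in the denominator as a non-event or drops out of it.

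No futility interim is planned, so the TOX rule is the only numerical rule that can stop the trial.

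The text headed Withdrawal from Study, within section 8.2.4, makes participation voluntary and lets a man end it whenever he chooses. It also requires the reason for a withdrawal to be documented.

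**The concern.** The definition turns on an adverse event that stops the operation from taking place. The exclusion turns on how the man left, whatever his reason. The two overlap in a man who has a serious adverse event, decides to leave because of it, and does not have the planned prostatectomy. He is the kind of case the rule was built to detect, yet someone applying the exclusion as written would record no TOX.

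The stopping probabilities in Table 2 of section 6.3 apply to the rate that is counted. If some true TOX cases are not counted, those probabilities overstate the protection at a given true rate of surgery-preventing toxicity.

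Other safety provisions do not replace the rule:

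- Section 6.2 keeps every treated man in the safety data, but that analysis is descriptive.
- The summary sent to the Medical Monitor every five patients has no numerical threshold. It is triggered by evaluable men who complete 24 weeks, so early leavers do not trigger it.
- Under section 8.2.4, capture of serious adverse events runs to 30 days after the last dose but ends if consent is withdrawn.

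**Working it through.** **Inputs from the documents**

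- Prior: "a beta(0.6, 1.4) distribution was assumed for the prior" (section 6.3).
- Threshold: stop if Pr(θ > 0.30 | data) > 0.90 (section 6.3).
- Looks: every 5 patients (Table 1 of section 6.3), to a maximum of 45 (section 6).
- Share f of true TOX cases recorded as voluntary leavers: not given. **Assumed** to be 10%, 25% or 50%.

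**Step 1. Reproduce the boundaries.** With x TOX among n men, the posterior is Beta(0.6 + x, 1.4 + n − x). The boundary is the smallest x whose posterior probability above 0.30 exceeds 0.90. At n = 5, x = 4 gives 0.975 and x = 3 gives 0.875, so the boundary is 4. Over all looks the boundaries are 4/5, 6/10, 8/15, 9/20, 11/25, 13/30, 15/35, 16/40 and 18/45. All nine match Table 1.

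**Step 2. Reproduce the operating characteristics.** An exact binomial recursion over the looks, counting a stop at n = 5 to 40 as early, gives:

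| True rate | Stop early, recomputed | Stated | Mean N, recomputed | Stated |
|---|---|---|---|---|
| 0.1 | 0.0006 | 0.0006 | 44.98 | 44.98 |
| 0.2 | 0.022 | 0.02 | 44.32 | 44.32 |
| 0.3 | 0.212 | 0.21 | 39.70 | 39.70 |
| 0.4 | 0.657 | 0.66 | 28.55 | 28.55 |
| 0.5 | 0.946 | 0.95 | 17.57 | 17.57 |

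The rule's arithmetic is sound. The open question is what gets counted.

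**Step 3. Counted rate under the exclusion.** Let q be the true TOX rate.

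- Leavers kept as non-events: counted rate = q(1 − f).
- Leavers dropped from the denominator: counted rate = q(1 − f) / (1 − qf).

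For q = 0.40 and f = 0.25 these are 0.40 × 0.75 = 0.30, and 0.30 / (1 − 0.10) = 0.333.

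**Step 4. Probability of stopping early at the counted rate.**

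| True rate q | Share f | Counted rate, kept | Stop early, kept | Counted rate, dropped | Stop early, dropped |
|---|---|---|---|---|---|
| 0.40 | 0 | 0.40 | 0.66 | 0.40 | 0.66 |
| 0.40 | 10% | 0.36 | 0.47 | 0.375 | 0.54 |
| 0.40 | 25% | 0.30 | 0.21 | 0.333 | 0.35 |
| 0.40 | 50% | 0.20 | 0.02 | 0.25 | 0.08 |
| 0.50 | 0 | 0.50 | 0.95 | 0.50 | 0.95 |
| 0.50 | 10% | 0.45 | 0.84 | 0.474 | 0.90 |
| 0.50 | 25% | 0.375 | 0.54 | 0.429 | 0.77 |
| 0.50 | 50% | 0.25 | 0.08 | 0.333 | 0.35 |

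With leavers kept, mean enrolment at a true rate of 40% rises from 28.55 to 33.53, 39.70 and 44.32 across the three shares. The dropped columns take looks after every five counted men, up to 45 counted.

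**Step 5. Low true rates.** At q = 0.10 the rule stops with probability 0.0006 when every TOX is counted. Undercounting can only lower a figure that is already negligible.

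**The case against.** The case for leaving the text alone has real substance.

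- **The group is small.** Stopping the drug for toxicity is not TOX. Section 8.1.3 sends men whose drug is held too long for toxicity through the pre-operative procedures and on to surgery, and the discontinuation criteria in section 8.2.4 have such men followed to the pre-operative visit. Most toxicity discontinuations are therefore protocol-directed and not voluntary departures. This stands.
- **The wording may not override.** No precedence is stated, and the word for a voluntary departure could be meant to set apart men who choose to go from men medically unable to have surgery. The closing condition about having surgery could also be read as covering both excluded groups, which would remove most of the problem. The comma and the 'or' make that reading less natural, and it fits poorly with men who have left the trial. If it was intended, the sentence still needs rewording.
- **High rates look unlikely.** Section 2.5 reports that 94% of men on monotherapy with a related drug completed 25 weeks. Its Table 4 shows 7.5% discontinuing that drug for adverse events in a trial in castrate-resistant disease. Both are broader than TOX and far below 30%. This stands as to likely impact, but a stopping rule exists for the case where such expectations fail.

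A reader might also infer more than the documents support:

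- *That leavers dilute the rate as non-events.* The denominator is not stated, so both versions are shown.
- *That the undercount is worst when toxicity is worst.* Nothing in the documents links the share leaving to the toxicity rate.
- *That protection is lost at a true rate of 30%.* The rule targets rates above 0.30, so a low stopping probability at exactly 30% is not a failure.
- *That "A patient may withdraw from study treatment phase for any reason" describes this route.* That sentence concerns the treatment phase. A man who stops only treatment can still have surgery and be assessed for TOX.
- *That these men disappear from safety oversight.* They stay in the safety population, and serious events go to the IND Office and the drug supplier while consent lasts. What they can be missing from is the stopping rule.

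**Conclusion.** The point holds as a gap in the event definition. Read literally, section 6.3 lets a surgery-preventing adverse event go uncounted when the man concerned is recorded as leaving voluntarily. The direction is certain: any such case lowers the TOX count.

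The size is unknown, because the documents give no share of TOX cases that would be recorded this way. The Step 4 figures are illustrations. They rest on assumed shares of 10% to 50%, a constant share across men, and true rates of 40% and 50%. Within those assumptions the loss ranges from slight (0.95 to 0.90) to near-total (0.66 to 0.02). If toxicity is as low as the related-drug figures suggest, the wording will make no practical difference.

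The change is still worth making before monitoring relies on the rule, because the repair costs almost nothing.

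**What to change.** Replace the exclusion sentence in section 6.3 with wording such as:

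> *Patients who leave the trial before surgery for reasons unrelated to an adverse event, or whose dose is reduced and who then have surgery, are not counted as TOX. A patient who leaves because of an adverse event and does not undergo the planned prostatectomy is counted as TOX. The denominator is all treated patients with a known TOX status.*

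Classify each departure from the reason already documented under Withdrawal from Study, and have the Medical Monitor, who already receives the five-patient summaries, confirm it. This rests on the recorded reason and on whether the operation took place, so nobody has to judge afterwards whether the event would have prevented it. A man whose surgical outcome cannot be learned after he leaves has unknown status and should be listed as such in the summary.

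The prior, the threshold, the Table 1 boundaries, the sample size and the visit schedule do not change. Table 2 then applies to the rate the rule is meant to monitor. The cost is a slightly higher counted TOX rate, since a man who leaves because of an adverse event and forgoes surgery partly by choice would now count.

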7. OUTLINE OF PATIENT ASSESSMENTS

7.1. Visit Schedule

A. Screening Phase:

- 1) Screening (day -30 to -1):
 - Signed Informed Consent
 - Medical history
 - Physical exam with Digital Rectal Exam (DRE)
 - Vital signs
 - ECOG Performance Status
 - Laboratories (Serum chemistry and hematology):
 - albumin, calcium, lactate dehydrogenase (LDH), sodium, potassium, chloride, magnesium, carbon dioxide, creatinine, BUN, AST, ALT, alkaline phosphatase, total bilirubin, total protein, glucose. Complete blood count.
 - Blood Coagulation profiles:
 - Prothrombin Time (PT)
 - Partial Thromboplastin Time (PTT)
 - Thyroid Stimulating Hormone (TSH) (T3 and T4 only to be done if TSH is abnormal)
 - Prostate-Specific Antigen (PSA) Test and Testosterone
 - Blood collection for Correlative Studies
 - EKG
 - MRI of the pelvis (as per physician discretion)

- Optional—Repeat prostate biopsy at MDACC if the initial biopsy was performed outside—per treating Urologist discretion, and optional tissue collection.
- Concomitant Medications Review
- Adverse Events
- EPIC Quality of Life (QOL) Questionnaire

B. Treatment Phase:

- 1) Week 1 Procedures: (If week 1 occurs within 2 weeks after screening visit, these procedures will not need to be repeated)
 - Physical exam with DRE if indicated by the treating physician
 - Vital signs
 - ECOG Performance Status
 - Laboratories (Serum chemistry and hematology)
 - Thyroid Stimulating Hormone (TSH) (T3 and T4 only to be done if TSH is abnormal)
 - Prostate-Specific Antigen (PSA) Test and Testosterone
 - Concomitant Medications Review
 - Adverse Events
 - Medication Dispensing (neoadjuvant apalutamide)

2) Week 5 Procedures (± 3 days):

- Medication dispensing (neoadjuvant apalutamide)
- Dosing compliance
- Physical exam with DRE if indicated by treating physician
- Vital signs
- ECOG Performance Status
- Laboratories (Serum chemistry and hematology)
- Thyroid Stimulating Hormone (TSH) (T3 and T4 only to be done if TSH is abnormal)
- Prostate-Specific Antigen (PSA) Test and Testosterone
- Concomitant Medications Review, Adverse Events
- Adverse Events

3) Week 9 Procedures (± 3 days):

- Medication dispensing (neoadjuvant apalutamide)
- Dosing compliance
- Physical exam with DRE
- Vital signs
- ECOG Performance Status
- Laboratories (Serum chemistry and hematology)

- Thyroid Stimulating Hormone (TSH) (T3 and T4 only to be done if TSH is abnormal)
- Prostate-Specific Antigen (PSA) Test and Testosterone
- Concomitant Medications Review
- Adverse Events

Note: At the mid-way evaluation (week 9), patients who fail to reach a 50% decrease in PSA, or demonstrate suspicious changes in DRE will be considered non-responders and recommended for early surgery.

4) Week 12 Procedures (± 3 days):

Optional: Repeat prostate biopsy per urologist's discretion. Acceptable to perform at the week 9 or week 17 visit if requested for patient travel needs.

5) Week 17 Procedures (± 3 days):

- Medication dispensing (neoadjuvant apalutamide)
- Dosing compliance
- Physical exam with DRE if indicated by treating physician
- Vital signs
- ECOG Performance Status
- Laboratories (Serum chemistry and hematology)
- Thyroid Stimulating Hormone (TSH) (T3 and T4 only to be done if TSH is abnormal)
- Prostate-Specific Antigen (PSA) Test and Testosterone
- Concomitant Medications Review
- Adverse Events
- EPIC Quality of Life (QOL) Questionnaire
- Blood collection for Correlative Studies

6) Week 24/ Pre-op/ End of Treatment Visit Procedures (± 3 days):

- Dosing compliance
- Physical exam with DRE
- Vital signs
- ECOG Performance Status
- Laboratories (Serum chemistry and hematology)
- Thyroid Stimulating Hormone (TSH) (T3 and T4 only to be done if TSH is abnormal)
- Prostate-Specific Antigen (PSA) Test and Testosterone
- Concomitant Medications Review
- Adverse Events
- EPIC Quality of Life (QOL) Questionnaire

- Blood collection for Correlative Studies
- 7) Radical Prostatectomy (2 weeks (+/-7 days) after last dose of study drug):
 - Perioperative data collection
 - Pathology Tissue Collection

C. Follow-up Phase:

- 1) Post Radical Prostatectomy: (within 30 days post-op +/- 3 days)
 - Physical exam and DRE if indicated by treating physician
 - Assess complications from surgery at 30 days using Clavien methodology (Table 5).
 - Adverse Events
 - Epic Quality of Life (QOL) Questionnaire
 - PSA, testosterone
- 2) Six Months Post-Radical Prostatectomy: (+/- 4 weeks)
 - a. Update complications to 90 day window
 - b. Use of adjuvant/salvage therapies
 - c. EPIC Quality Of Life (QOL) Questionnaire
 - d. PSA, testosterone
- 3) Twelve Months Post Radical Prostatectomy—Last on-site Study Visit: (+/- 4 weeks)
 - a. EPIC Quality Of Life Questionnaire
 - **b.** PSA, testosterone
 - c. Use of adjuvant/salvage therapies
 - d. Update complications
- 4) Post Study Follow-up Data Collection (on-site or remote): (+/- 4 weeks)
 - **a.** Intervals 24, 36, 48, 60 months
 - **b.** PSA/biochemical relapse-free status
 - **c.** Use of adjuvant/salvage therapies
 - d. Update complications
 - e. Epic Quality of Life (QOL) Questionnaire

7.2 Details of Assessment Methods:

7.2.1 QOL assessments per above: may be written or via tablet. Surveys will consist of the Expanded Prostate Cancer Index (EPIC), including the SF-12. As an alternative, the data may be collected using an electronic tablet method. Any post-operative surveys occurring after the incidence of additional post radical prostatectomy radiation or hormonal therapy will continue but be so designated for analysis.

2015-0693 June 10, 2022 Page 21

7.2.2 Complications: use Clavien reporting system shown in Table 5.

Table 5: Classification of Surgical Complications [34]

Grades	Definition
Grade I	Any deviation from the normal postoperative course without the need for pharmacological treatment or surgical, endoscopic and radiological interventions. Allowed therapeutic regimens are: drugs such as antiemetics, antipyretics, analgesics, diuretics and electrolytes, and physiotherapy. This grade also includes would infections opened at the bedside.
Grade II	Requiring pharmacological treatment with drugs other than such allowed for grade I complications. Blood transfusions and total parenteral nutrition are also included.
Grade III	Requiring surgical, endoscopic or radiological intervention
Grade IIIa Grade IIIb	Intervention not under general anesthesia. Intervention under general anesthesia.
Grade IV	Life-threatening complication (including CNS complications)* requiring IC/ ICU management.
Grade IVa Grade IVb	Single organ dysfunction (including dialysis) Multiorgan dysfunction
Grade V	Death of a patient
Suffix "d"	If the patient suffers from a complication at the time of discharge, the suffix "d" (for "disability") is added to the respective grade of complication. This label indicates the need for a follow-up to fully evaluate the complication.
excluding trans	nage, ischemic stroke, subarachnoid bleeding, but sient ischemic attacks, CNS, central nervous system; IC, are; ICU, intensive care unit.

2015-0693 June 10, 2022 Page 22

Table 6: Study Calendar

Evaluation	Screeninga	Wk 1	Wk 5	Wk 9	Wk 12	Wk 17	Wk 24/ Preop ^h	Surgery	30 d post op	6 mo	12 mo	2 yr	3 yr	4 yr	5 yr
			+/- 3 days		+/- 3 days	+/- 4 wks	+/-4 wks	+/-4 wks	+/-4 wks	+/- 4 wks	+/-4 wks				
Medical History	Х														
Physical Exam w/DRE	Х	Хр	Χp	Х		Хр	Х		Χþ						
Vital Signs	Х	Х	Χ	Χ		Х	Х								
ECOG PS	Х	Χ	Χ	Χ		Χ	Х								
EKG	Х														
MRI Pelvis	Χi														
Concomitant Medication	Х	Х	Х	Х		Х	Х			Xc	Xc	Xc	Χc	Xc	Xc
AE	Х	Х	Х	Χ		Х	Х		Х						
Dosing compliance			Х	Х		Х	Х								
Serum chemistry/ hematology ^d	Х	Х	Х	Х		Х	Х								
PT/PTT	Х														
TSH ^e	Х	Х	Х	Χ		Х	Х								
PSA	Х	Х	Х	Х		Х	Х		Х	Х	Х	Х	Х	Χ	Χ
Testosterone	Х	Х	Х	Х		Х	Х		Х	Х	Х				
EPIC QOL	Х					Х	Х		Х	Х	Х	Х	Х	Χ	Χ
Blood Correlative Studies ⁱ	Х					Х	Х								
Tissue procurement	Χ ^f				Xf			Х							
Complications, post op therapy ⁹									Х	Х	Х	Х	Х	Х	Х

- a: Within 30 days prior to initiation of study treatment
- b: Physical exam and DRE if indicated by treating physician
- c: Use of adjuvant/salvage therapies only, such as hormones or radiation
- d: albumin, calcium, lactate dehydrogenase (LDH), sodium, potassium, chloride, magnesium, carbon dioxide, creatinine, BUN, AST, ALT, alkaline phosphatase, total bilirubin, total protein, glucose, complete blood count with differential
- e: T3/T4 testing to be done if abnormal TSH or clinically indicated
- f: Optional collection of tissue for research purposes at time of prostate biopsy at baseline and week 12, if indicated by treating physician. If patient is not available to return to clinic on week 12 for repeat biopsy, this could be done either during week 9 or week 17 visits. Please note that tissue collection at time of radical prostatectomy is mandatory
- g: Record post-operative complications using Clavien method within 30 days and 90 days, and any long-term complications related to surgery.

- h: Early treatment discontinuation patients will complete all the pre-op assessments within 30 days post treatment discontinuation as their last study visit
- i: Including plasma, whole blood and serum samples as indicated in section 9.1
- j. As per physician discretion

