4. INVESTIGATIONAL PLAN

This is a single center, phase II, open label, pre-operative study of apalutamide in patients with intermediate risk prostate cancer. The study period will consist of screening, treatment, and follow-up visits to 12 months post-operative. Additional follow-up onsite or via remote contact will determine disease-free and treatment-free status at yearly intervals 2-5. Surgery will occur within 2 weeks of completing 24 weeks of apalutamide. At the mid-way evaluations (weeks 9 or 12), patients who fail to reach a ≥50% decrease in PSA, or demonstrate suspicious changes in DRE will be considered non-responders and recommended for early surgery. For responders, the plan calls for 5 pre-operative PSA measurements that will be analyzed for rate of decline and nadir. In the post-treatment evaluation, patients will be off formal protocol at 12 months, however the investigating team will track PSA measurements for biochemical failure rates at 2, 3, 4 and 5 years (outside or inside measurements) using >0.2 ng/mL as the failure definition.

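### Table 6 footnote h ends study visits at the pre-op assessment for men who stop apalutamide early, which contradicts the post-operative schedule for those who then have prostatectomy

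*Combined protocol and SAP*

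**What the plan says.** Footnote h is attached to the Week 24/Preop column of Table 6 and reads: "Early treatment discontinuation patients will complete all the pre-op assessments within 30 days post treatment discontinuation as their last study visit". It does not separate men who go on to surgery from men who do not.

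Under Criteria for Discontinuation of Study Treatment, the bullets on sustained toxicity, dosing non-compliance, new anticancer treatment and prohibited medication each say that the man is followed to the pre-op visit. They say nothing about what comes after it. The bullet for week 9 PSA or DRE failure does not carry this wording.

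Other parts of the plan expect these men to have surgery and post-operative follow-up:

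- Week 9 non-responders "will be considered non-responders and recommended for early surgery" (section 7.1). Section 8.1.3 has men who are off drug for more than 30 days because of toxicity scheduled for surgery.
- Footnote g, in the same table, says: "Record post-operative complications using Clavien method within 30 days and 90 days". It exempts no one.
- Section 7.1 sets post-operative visits at 30 days, 6 months and 12 months, and labels the 12-month visit "Last on-site Study Visit". Section 4 says "patients will be off formal protocol at 12 months".
- Section 6.2 makes men with at least 9 weeks of drug plus prostatectomy evaluable for the primary endpoint.
- Sections 3.2 and 6.1.2 set secondary objectives on the safety of apalutamide followed by prostatectomy, and on recurrence and quality of life in treated patients. Neither is limited to men who complete 24 weeks.

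**The concern.** The same calendar tells staff two different things about a man who stops the drug early and then has his prostate removed. Footnote h ends his study visits before the operation. Footnote g and section 7.1 expect data on him afterwards.

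These men are not a random subset. They stop because PSA did not fall enough, because of toxicity, or because of poor compliance. If staff follow footnote h, then 30- and 90-day complications, post-operative EPIC scores, and PSA, testosterone and adjuvant or salvage therapy through month 12 will be missing for exactly this group. If staff follow footnote g and section 7.1, the data will be there. Section 6.2 does not say which is intended, so the population behind the post-operative secondary results depends on how the footnote is read.

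**Working it through.** **1. Does any text resolve the conflict?** Setting the places side by side:

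| Place | What it implies for an early stopper who has surgery |
|---|---|
| Table 6, footnote h | Pre-op assessment is his final study visit |
| Discontinuation criteria, four bullets | Followed to the pre-op visit; silent afterwards |
| Table 6, footnote g | Clavien recording at 30 and 90 days |
| Section 4 | Visits to 12 months after surgery; no one excluded |
| Section 7.1, follow-up phase | Visits at 30 days, 6 and 12 months; no one excluded |
| Section 6.2 | In the primary analysis if he had at least 9 weeks of drug |
| Withdrawal from Study | Even when consent is withdrawn, whether this covers post-prostatectomy data must be clarified |

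No sentence defines the final study visit in footnote h as the final visit of the treatment phase, and none exempts men who have surgery.

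**2. What the literal reading removes.** Counting Table 6 marks in the 30-day, 6-month and 12-month columns:

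- PSA 3, testosterone 3, EPIC 3, complications/post-op therapy 3: subtotal 12
- Concomitant medication row, limited there to adjuvant or salvage therapy, at 6 and 12 months: 2
- Adverse events at 30 days: 1
- Physical exam, if indicated, at 30 days: 1

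Total = 12 + 2 + 1 + 1 = 16 marks per man, over 3 visits. These include all 3 post-operative testosterone marks. They are also 3 of the 7 post-operative marks in each of the PSA, EPIC and complications rows. The other 4 in each row fall in years 2 to 5. Both Clavien windows of footnote g are lost, because section 7.1 assigns the 30-day assessment to the first visit and places "Update complications to 90 day window" at the 6-month visit.

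**3. Does adverse event reporting fill the gap?** Routine AE and SAE capture ends 30 days after the last dose at the latest (section 8.2.4), apart from later related SAEs. If the section 7.1 surgery window applies (14 ± 7 days after the last dose, so 7 to 21 days), capture ends 30 − 21 = 9 to 30 − 7 = 23 days after surgery. If the Radical Prostatectomy text applies (within 2 weeks, so 0 to 14 days), it ends 30 − 14 = 16 to 30 − 0 = 30 days after surgery. Neither comes near the 90-day window.

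**4. Size per man.** Let n men have surgery, m of them be unobserved after it, and x complications be seen among the n − m observed. With no assumption about the missing men, the rate among all n lies between x/n and (x + m)/n, a width of m/n.

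- n = 45 (full enrolment, all having surgery; an assumption): 1/45 = 2.2 percentage points per man
- n = 41 (the calculated sample size): 1/41 = 2.4 percentage points per man

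The documents give no value for m, so no total is offered.

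**5. What is not touched.** The primary endpoint is read from the surgical specimen, and footnote f makes tissue collection at prostatectomy mandatory. The stated 84% power does not depend on these visits. It reproduces as 84.8% for n = 41, rejecting at 8 or fewer men with adverse features, with a lower-tail error of 0.024 at 35%.

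**The case against.** The best reply is that footnote h means the last visit of the treatment phase, and much supports this. The footnote hangs on a column that section 7.1 titles as the end-of-treatment visit and places under the treatment phase, with follow-up in a separate block. Section 8.1.3 and the discontinuation criteria take men off the treatment phase, while withdrawal from the study has its own heading. The footnote cannot be fully literal either: it would then also strike the surgery step, where tissue collection is mandatory. It may have been written mainly for men who never reach surgery, who have no post-operative visits to lose. All of this makes the benign reading plausible. It does not make it stated, and the bullets that follow men to the pre-op visit fit the literal reading just as well.

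Four stronger inferences are tempting, and the documents do not support them:

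- **That the visits will certainly be lost.** The text contradicts itself. It does not settle the matter against follow-up.
- **That years 2 to 5, and so the 3-5 year recurrence rate, are lost.** Sections 4 and 7.1 treat that period as data collection after the study, from on-site or remote sources. Whether footnote h reaches it is unclear.
- **That every EPIC comparison drops these men.** Footnote h itself requires the full pre-op assessments, which include EPIC, so a baseline to end-of-treatment pair survives. Section 6.2 names no time point; only a comparison using a post-operative score would lose them.
- **That about four men are affected.** The difference 45 − 41 = 4 is an enrolment allowance for compliance, not a forecast of early stops, and it does not count week 9 non-responders.

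**Conclusion.** The contradiction is real and should be reconciled. Footnote h and the four discontinuation bullets stop at the pre-op visit with no exception for men who have prostatectomy. Footnote g, sections 4 and 7.1, the evaluability rule in section 6.2 and the secondary objectives all point the other way.

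If the footnote is followed literally, each early stopper who has surgery loses three visits and 16 scheduled marks. Each also leaves a post-operative complication rate for all treated men undetermined by 2.2 percentage points, assuming all 45 have surgery. The number of such men is unknown, as are the size and direction of any bias. The effect is confined to secondary endpoints.

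**What to change.** Reconcile footnote h and the four discontinuation bullets with footnote g, sections 3.2, 4, 6.1.2, 6.2 and 7.1, and the Withdrawal from Study text. One way:

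- In footnote h and the bullets, call the pre-op assessment the last treatment-phase visit.
- Add that men who undergo prostatectomy keep the existing Table 6 post-operative data schedule (30 days, 6 and 12 months, and the year 2 to 5 collection) unless they withdraw consent to that collection.
- In section 6.2, state that these men are included in the Kaplan-Meier, post-operative EPIC and complication analyses.

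The cost is a wording amendment. There is no new procedure and no change to treatment or stopping rules. A few more men would complete up to three visits each that are already in the calendar.
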